We estimate a total sample size of 1080 children with SAM (360 per arm) and 1080 children with MAM (360 per arm) will provide at least 90% statistical power to demonstrate non-inferiority for each comparison, with a non-inferiority margin of 10 percentage points, assuming a recovery rate in the control of 77% (Table 4). For relapse outcomes, sample size will be smaller, and thus power will be lower, because only recovered children will be included in the analysis. All calculations assume a one-sided $\alpha = 0.05$ for non-inferiority and two-sided $\alpha = 0.05$ for superiority analyses.

Table 4. Sample size calculations

Scenarios with at least 80% power are **bolded**.

Primary outcome	Analysis type	Sample size per arm	Outcome prevalences reported in literature	Non-inferiority margin or detectable effect size	Assumption on control group outcome prevalence/means in sample size calculations	Power per comparison
Anthropometric recovery at discharge	Non-inferiority	360 MAM and 360 SAM children/arm enrolled; 306 MAM and 306 SAM children in analysis after 15% attrition	MAM recovery (with RUSF*): 73% (13); 73% (14); 85% (15) SAM recovery : 55.4% (16); 82.3% (17); 76% (18); 71% (pooled estimate from meta-analysis) (19)	10 percentage points (absolute difference)	55.4% (vs 45.4%)	85.6%
					77.0% (vs 67.0%)	90.0%
					82.3% (vs 72.3%)	96.8%
Relapse to wasting within 3-months post-discharge	Superiority	236 children/arm in analysis (assuming 77% of the 306 children recover)	Post-MAM relapse : 30% within 3 months (period prevalence) (20); 33% within 12-months (21) Post-SAM relapse : 6.8% 3-month cumulative incidence (22); 24% 2-month cumulative incidence (23); 30% within 3-months (unpublished); 2.6 episodes per child-year (unpublished); 1.3	35% relative reduction (incidence rate ratio = 0.65)	Incidence of 2.6 episodes per child-year	80.0%
					Prevalence of 30% (vs 20%)	71.0%

			episodes per child-year (unpublished)			
--	--	--	--	--	--	--

*RUSF = ready-to-use supplementary food

Study procedures

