All analyses will be delineated in detail in the trial Statistical Analysis Plan (SAP) which will be developed and finalized prior to initiation of enrollment. A summary is given here.

The study is powered for separate comparisons between (i) the control group and SMS-RUTF, and (ii) between the control group and S-RUTF. All analyses will be stratified by MAM vs SAM status.

Baseline characteristics will be assessed with descriptive statistics (means and standard deviations for continuous variables, and proportions for categorical variables). Baseline characteristics will be adjusted for in the analyses if it is both (i) associated with treatment outcomes or relapse in published literature and (ii) imbalanced between treatment arms as determined by statistically significant t-test or χ^2 tests with 5% significance level.

For binary outcomes, we will use log-binomial regression to estimate relative risks (RRs) and 95% confidence intervals (CIs) for the RRs, adjusting for any baseline factors as appropriate. Non-inferiority will be declared if the lower bound of a one-sided 95% CI for the RR lies entirely below the non-inferiority margin of a relative 12.5%. For continuous outcomes, we will use linear regression to estimate differences in that outcome between treatment arms, adjusting for any baseline factors as appropriate. For superiority analyses (relapse), we will use a two-sided 95% CI and superiority will be declared if the lower bound of the 95% CI for the relative risk is above 1.0.

Non-inferiority analyses can be spuriously favored by ITT analyses because non-compliance diminishes any treatment effects, thus biasing the effect size toward the null (35). We will therefore repeat all non-inferiority analyses with a per-protocol (PP) population, restricting the analyses to only children who comply with their full treatment course, per caregiver report. The ITT and PP results will be presented side-by-side for non-inferiority analyses; superiority analyses will be analyzed as ITT only.

Adverse event (AE) and serious adverse event (SAE) monitoring and reporting

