## Hypotheses and Objectives

### Main trial

1. To assess the non-inferiority of novel soy-maize-sorghum (SMS-) RUTF and soy-based (S-) RUTF on treatment recovery to standard RUTF  
Hypothesis: MAM and SAM children who received SMS-RUTF or S-RUTF during treatment will have non-inferior recovery rates, compared to those who received standard RUTF.
2. To assess the superiority of SMS-RUTF and S- RUTF on post-recovery relapse compared to standard RUTF  
Hypothesis: MAM and SAM children who received SMS-RUTF or S-RUTF during treatment will have lower relapse rates compared to children who received standard RUTF.

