## Study outcomes

### Main trial

The primary and secondary outcomes for the main trial and their definitions are listed in Table 1. Outcomes are the same for MAM and SAM children.

*Table 1. Primary and secondary efficacy outcomes*

Outcomes	Definition	Type of analysis
Primary outcomes		
Anthropometric recovery at discharge	WLZ $\geq$ -2 and MUAC $\geq$ 125 mm and absence of bilateral pitting edema for two consecutive visits, at the day of end of treatment	Non-inferiority
Relapse to wasting within 3 months post-discharge	A new episode of wasting (defined as WLZ/WHZ $<$ -2 or MUAC $<$ 125 mm or presence of bilateral pitting edema) within the 3-month period following recovery from the index wasting episode, among children who recovered from their index episode	Superiority
Length of stay (LOS) among recovered children	The number of days between the day the child is admitted to treatment and the day the child is determined to be recovered and thus discharged from treatment	Non-inferiority
Weight gain	Change in child's weight (gram/kilogram/day) between weight on day of admission to treatment and the day of end of treatment	Non-inferiority
Anthropometry at discharge from treatment	WLZ/WHZ, MUAC, weight, height/length, LAZ/HAZ and WAZ at the day of end of treatment	Non-inferiority
Anthropometry at 3-months post-discharge	WLZ/WHZ, MUAC, weight, height/length, LAZ/HAZ and WAZ at 3-months post-discharge (3 months after the day of end of treatment)	Superiority
Hemoglobin at discharge	Hemoglobin concentration (grams/liter) at the day of end of treatment	Non-inferiority
Hemoglobin at 3-months post-discharge	Hemoglobin concentration (grams/liter) at 3-months post-discharge (3 months after the day of end of treatment)	Superiority
Secondary outcomes		
Default from treatment	Child is absent for two consecutive visits, declared a defaulter on the second visit	Non-inferiority

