### Sample size and statistical power

#### Main trial

We estimate a total sample size of 1080 children with SAM (360 per arm) and 1080 children with MAM (360 per arm) will provide sufficient statistical power to demonstrate non-inferiority for each comparison, with a non-inferiority margin of relative 12.5%, assuming a recovery rate in the control of 76% and a loss to follow up of 15% (Table 4). The sample size will be smaller for analyses of relapse, because only recovered children will be included in the analysis. All calculations assume a one-sided  $\alpha = 0.05$  for non-inferiority and two-sided  $\alpha = 0.05$  for superiority analyses,  $\beta = 0.8$ , and 15% attrition. While the key objectives of this research are to evaluate effects of the alternative RUTFs on recovery and relapse, we consider as primary outcomes any outcome for which we have adequate power for clinically or policy meaningful effect sizes (5).

 Stata commands `ssi` for continuous outcomes and `artbin` for binary outcomes were used for non-inferiority analyses, and `power twomeans` for continuous outcomes and `power twoproportions` for binary outcomes were used for superiority analyses. Outcome proportions, means, or standard deviations were taken from relevant studies in literature as delineated in Table 4.

Table 4. Calculations of detectable effect sizes for all outcomes

Outcome	Outcome prevalence in the literature	Type of analysis	Non-inferiority margin (relative) with $\geq 80\%$ power (Non-inferiority)	Detectable effect size at 80% power (Superiority)	Rank of outcome
Anthropometric recovery at discharge	MAM recovery (with RUSF*): 73% (6); 73% (7); 85% (8)  SAM recovery: 55.4% (9); 82.3% (10); 76% (11); 71% (pooled estimate from meta-analysis) (12)	Non-inferiority	12.5% relative margin		Primary
Relapse to wasting within 3-months post-discharge	Post-MAM relapse: 30% within 3 months (13); 33% within 12-months (14)  Post-SAM relapse: 6.8% 3-month cumulative incidence (15); 24% 2-month cumulative incidence (16); 30% within 3-months (unpublished)	Superiority		Risk difference of 11%; Relative risk = 0.72	Primary
Length of stay (LOS) among recovered children	MAM: 36.4 days (SD 50.4 days)(17); 5.9 weeks (95% CI: 4.9, 7.0)(18) SAM: 56 days (assumed 41 day SD) (9)	Non-inferiority	MAM: 4.9 days; 12.5% relative margin SAM: 8 days; 12.5% relative margin		Primary

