## Statistical methods

We will conduct two separate comparisons between (i) the control group and SMS-RUTF, and (ii) between the control group and S-RUTF. All analyses will be done separately by wasting severity status (MAM vs SAM); that is, all analyses will be conducted and presented among MAM children and among SAM children separately. No adjustments for multiple comparisons will be made.

For binary outcomes, we will use log-binomial regression to estimate relative risks (RRs) and 95% confidence intervals (CIs) for the RRs, adjusting for any baseline factors as appropriate (described further below). If the regression model is adjusted, we will present both crude (unadjusted) and adjusted model results. If the models do not converge, we will use Poisson regression models with robust estimation of standard errors (26) and report which model was used. Non-inferiority will be declared if the lower bound of a one-sided 95% CI for the RR lies entirely below the non-inferiority margin of a relative 12.5%. For superiority analyses, we will use a two-sided 95% CI and superiority will be declared if the lower bound of the 95% CI for the relative risk is above 1.0. All analyses will be adjusted for health center to reflect the stratified randomization (27–29).

For continuous outcomes measured at one timepoint, we will use linear regression to estimate differences in that outcome between treatment arms, adjusting for any baseline factors as appropriate and health center (as explained above). Both unadjusted and adjusted model results will be presented.

For any outcome for which non-inferiority is demonstrated, we will then sequentially test for superiority. In these cases, we will report both non-inferiority and superiority results. The superiority analysis will be considered exploratory, as the study power calculations were based on non-inferiority effect size.

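### The superiority rule points the wrong way for relapse: as written, only significantly more relapse on a new product would meet it

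*SAP*

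**What the plan says.** The SAP, Statistical methods, gives one superiority rule for binary outcomes, using a two-sided 95% confidence interval: "superiority will be declared if the lower bound of the 95% CI for the relative risk is above 1.0". The Protocol, Statistical analysis, has the same rule and names the outcome: "For superiority analyses (relapse), we will use a two-sided 95% CI and superiority will be declared if the lower bound" exceeds 1.0. Neither document has a separate rule for adverse outcomes, and neither says which arm is the numerator of the relative risk.

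The direction of benefit is clear elsewhere. In SAP Table 1 relapse begins as "A new episode of wasting" among recovered children, so it is an adverse event. The SAP's hypothesis is that children given either new product "will have lower relapse rates compared to children who received standard RUTF". The planned effect in SAP Table 4 is "Risk difference of 11%; Relative risk = 0.72". The same table plans RR 0.34 for relapse to SAM and 0.689 for relapse to MAM. Protocol Table 4 plans an incidence rate ratio of 0.65, described as a 35% reduction, and a comparison of 30% with 20%.

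The SAP also sends any outcome that shows non-inferiority on to an exploratory superiority test. It gives no confidence-limit rule for superiority on continuous outcomes.

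**The concern.** A lower confidence limit above 1.0 for an intervention-to-control relative risk means that the event is significantly more frequent on the intervention. For relapse that is harm. SAP Table 1 plans superiority for four binary outcomes (relapse to wasting, relapse to SAM, relapse to MAM, anemia at 3 months). All four are adverse, so the rule is reversed for each of them. It suits only favourable binary outcomes, namely recovery and adherence, and those reach a superiority test only through the exploratory step after non-inferiority.

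This is the decision rule for the second primary objective. A superiority finding on relapse also opens the cost-per-DALY model (Protocol, Costing; SAP, Sub-study 3: Costing). Followed to the letter, the plan could not declare the benefit it was designed to detect. If an analyst silently reversed the rule after seeing results, that would be an undocumented departure from a pre-specified primary criterion.

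**Working it through.** **Inputs.**
- Children analysed for relapse: 236 per arm within each severity stratum (Protocol Table 4; 0.77 × 306 = 235.6).
- Planned relapse: 30% control, 20% intervention (Protocol Table 4).
- Alpha: 0.05 two-sided (Protocol, Sample size).
- SAP planned effect: risk difference 11 points, RR 0.72 (SAP Table 4).
- Assumption: RR = intervention/control, as the planned ratios imply.

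**Step 1. Reproduce the stated power.** Two-proportion z-test with pooled variance under the null:
- Null SE = √(2 × 0.25 × 0.75 / 236) = 0.0399.
- Alternative SE = √((0.30 × 0.70 + 0.20 × 0.80) / 236) = 0.0396.
- Power = Φ((0.10 − 1.96 × 0.0399) / 0.0396) = Φ(0.55) = 71.0%.

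This matches the 71.0% in Protocol Table 4.

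**Step 2. Expected interval at the planned effect.** With p_c and p_t the control and intervention proportions, SE of log RR = √((1 − p_c)/(n p_c) + (1 − p_t)/(n p_t)).
- SE = √(0.70/70.8 + 0.80/47.2) = 0.1638.
- log(0.20/0.30) = −0.4055.
- 95% CI = exp(−0.4055 ± 1.96 × 0.1638) = 0.48 to 0.92.

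The whole interval lies below 1. That is clear benefit, and it fails the written rule.

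**Step 3. Chance that each rule declares superiority.**
- Written rule, lower bound above 1: Φ(log RR/SE − 1.96).
- Corrected rule, upper bound below 1: Φ(−log RR/SE − 1.96).

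| Control vs intervention | RR | Expected 95% CI | Written rule | Corrected rule |
|---|---|---|---|---|
| 30% vs 20% (Protocol) | 0.67 | 0.48 to 0.92 | 0.000005 | 69.7% |
| 39.3% vs 28.3% (implied by SAP) | 0.72 | 0.56 to 0.93 | 0.000004 | 70.5% |
| 30% vs 30% | 1.00 | 0.76 to 1.32 | 2.5% | 2.5% |
| 30% vs 40% (illustrative harm) | 1.33 | 1.04 to 1.71 | 61.7% | 0.00001 |

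The second row solves the SAP's two figures together: 0.11/(1 − 0.72) = 39.3% control relapse. The last row is an illustration and is not planned in either document.

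**Step 4. Check by simulation.** In 400,000 simulated trials at 30% versus 20%, the written rule never declared superiority and the corrected rule did so in 70.6%. At 30% versus 40%, the written rule did so in 62.1%.

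**Step 5. Try the inverted ratio.** With RR = control/intervention, the planned effect becomes 1.50 with interval 1.09 to 2.07, and the written rule works. It would also turn the SAP's planned 0.72, 0.34 and 0.689 into planned harm, which contradicts the stated hypothesis.

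**The case against.** The strongest defence is that no competent analyst would be misled. The hypothesis, the planned ratios and the two-sided interval all make the intended direction plain, and the interval will be reported whatever the rule says. Much of this stands. The sentence reads like a slip carried from one document to the other. A reader might infer that the trial will in practice report harm as superiority. The documents do not support that, because it would require following one sentence against everything else they say about relapse. The probabilities above describe literal application and do not forecast conduct.

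A reader might also infer that the power calculation is undermined. It is not: a two-sided test has the same power whichever limit the text names, and the stated 71.0% reproduces.

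A second defence is that the numerator is undefined, so the ratio could be control over intervention. That is formally possible, but neither document says so, and SAP Table 4 points the other way.

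A third is that the rule is generic and meant for favourable outcomes. The Protocol rules this out by attaching it to relapse. Nor would it be right to say that the rule fits recovery alone: adherence is also favourable and can reach the exploratory superiority test.

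**Conclusion.** The rule is wrong as written in both documents for every pre-specified binary superiority outcome, and no other section corrects it. At the Protocol's planned effect, literal application gives essentially no chance of declaring superiority, where the corrected rule gives about 70%. With relapse raised from 30% to 40%, it would declare superiority about 62% of the time.

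These figures assume RR = intervention/control, 236 analysed children per arm, and an unadjusted Wald interval on the log scale. The planned log-binomial model adjusts for health center, which could move the percentages a little but cannot change the direction.

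The fault lies in the decision rule only. It must nevertheless be corrected before unblinding, because it governs a primary objective and triggers a further analysis.

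**What to change.** Amend SAP Statistical methods and Protocol Statistical analysis. Define the RR as intervention/control and differences as intervention minus control. Then state, each time with the two-sided 95% CI:

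- **Adverse binary outcomes** (relapse to wasting, SAM or MAM; anemia at discharge and at 3 months; default; transfer; non-response; morbidity; mortality): superiority requires the upper bound of the RR to be below 1.0.
- **Favourable binary outcomes** (recovery, adherence): superiority requires the lower bound of the RR to be above 1.0.
- **Continuous outcomes where higher is better** (weight gain, anthropometry, hemoglobin): superiority requires the lower bound of the difference to be above 0.
- **Length of stay**, where shorter is better: superiority requires the upper bound of the difference to be below 0.

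A single rule for all continuous outcomes, with the lower bound above 0, would not do. Length of stay can reach the exploratory superiority test, and a longer stay would then count as superior. A benefit-direction column in SAP Table 1 would settle every outcome in one place.

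The cost is small: no new data and no change to sample size. The SAP describes late enrolment in the past tense, so this is a late change. It should be dated and documented before the letter codes are released. The Protocol correction also has to go for ethical approval before it is implemented (Protocol, Trial registration).

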## Treatment of missing data

Wherever more than 10% of outcome observations are missing, we will report the number of observations used in the analysis. No imputation of missing data will be done, given the limited number of covariates available to predict missing observations. Every effort will be made to minimize attrition of study participants, thus keeping missing data to a minimum. Default from treatment will be considered a treatment outcome, rather than missing data.

## Analysis frame

Our primary analysis frame will be intention-to-treat (ITT). ITT groups will be defined by the randomization assignment to which participants are allocated; that is, all participants will be included in the analysis based on the treatment group to which they were randomized.

However, ITT analyses can bias effect sizes toward the null, spuriously demonstrating non-inferiority, because non-compliance diminishes any treatment effects (30). Despite this, ITT is still the recommended approach for non-inferiority trials (31). To mitigate this concern, we will conduct a secondary analysis in which we repeat all analyses with a Complier Average Causal Effects (CACE) approach. CACE analyses adjust for any differences between children who adhere vs do not adhere in characteristics that may influence outcomes, thus mitigating concerns of confounding. CACE analyses are also useful for superiority analyses, as these results can distinguish between the effects of the interventions themselves, and effects of the adherence to the interventions. Both ITT and CACE results will be presented. This is summarized in Table 5.

Adherence will be defined as attendance at all treatment visits. The characteristics to be considered for adjustment and the decision rules to determine whether adjustment will be made will be the same as described in the next section below.

*Table 5. Analysis approaches and sensitivity analyses by type*

Analysis type	Primary analysis	Secondary analysis	Sensitivity analyses
Non-inferiority	ITT	CACE	Exclusion of children who received both study products and standard of care products during treatment course
Superiority	ITT	CACE	Exclusion of children who received both study products and standard of care products during treatment course

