We will conduct one sensitivity analysis. There were children enrolled near the end of the study whose product was switched to standard of care product during their treatment course because the expiration date of the study products occurred during their treatment course. That is, they received the study product to which they were randomized for the majority of their treatment course, and then when the expiration date of that product neared, they received a standard of care product for the remainder of their treatment duration. As these children received both the study and standard of care products, including them in the study arm to which they were randomized represents misclassification and their inclusion could bias the results to the null. If we were to exclude only the children assigned to the expiring product, there is the potential to induce bias by excluding children with long treatment durations or poorer treatment outcomes in one treatment arm, making treatment outcomes spuriously appear worse in this arm. Therefore, we will conduct a sensitivity analysis excluding all children in all treatment arms who received product on or after the date on which this switch was made.

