### Sub-group and sensitivity analyses

We will conduct two *a priori* sub-group analyses for primary study outcomes only. These are for exploratory purposes, and our study did not factor these sub-groups into account in power calculations. We will assess all primary study outcomes separately among the following sub-groups of children:

1. Age group at enrollment: 6-23 months vs 24-59 months
2. Children with high-risk MAM, defined as MAM status at enrollment (defined as above) and any of the following characteristics:
  - a. Age 6-23 months
  - b. WAZ < -3
  - c. MUAC 115-119 mm
  - d. History of SAM
  - e. Present case of MAM is a relapse case

We hypothesize the alternative RUTFs may have a different effect in these sub-groups. First, if the alternative RUTFs impact the gut microbiome of children, these interventions may have greater impact on the anthropometry outcomes of younger children. The gut microbiome before three years of age is especially sensitive to external influences such as nutrition, and thus may represent a critical window in which interventions may have the most influence (32). Conversely, one study on a previous formula of SMS-RUTF reported lower efficacy among children 6-23 months of age (33), although a subsequent study reported non-inferiority of the SMS-RUTF product among this age group after it had been reformulated (19). Further data on the efficacy of this product within the subgroup of 6–23-month-old children is useful.

Children with MAM or SAM have microbiome profiles that are more immature for their age and this deleterious microbiome immaturity is inversely associated with WHZ even within MAM or SAM categories (34). Thus, we hypothesize that children with high-risk MAM may have gut microbiome profiles that are more suboptimal than their lower-risk MAM counterparts, and thus may stand to experience a stronger benefit from any microbiome influences exerted by the products. Additionally, release of new WHO guidelines on the prevention and management of wasting in 2023 recommend prioritize specialized food products (such as RUTF) for high-risk MAM (35), and thus efficacy data within this sub-group may be useful for policymakers in Burkina Faso in implementing these guidelines in the coming years.

As described above, we will conduct one sensitivity analysis, in which we exclude children whose treatment product was switched to the standard RUTF before the expiration date of their treatment product.

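### The SAP's only sensitivity analysis, for the product switch, is defined by two incompatible exclusion rules, and the bias of the rule in Table 5 is stated in the wrong direction

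*SAP*

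**What the plan says.** SAP, Statistical methods: "We will conduct one sensitivity analysis". It concerns children enrolled near the end of the study who received their randomized product for most of the course and a standard of care product for the rest. The section considers the narrow exclusion and rejects it: "If we were to exclude only the children assigned to the expiring product, there is the potential to induce bias". The reason it gives is that the children lost from that arm would be those who stayed longest or did least well, and it says that this would make the arm look worse than it is. It therefore chooses "excluding all children in all treatment arms who received product on or after the date on which this switch was made".

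SAP, Analysis frame, Table 5 gives the sensitivity analysis for both non-inferiority and superiority as "Exclusion of children who received both study products and standard of care products during treatment course".

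SAP, Sub-group and sensitivity analyses refers back to the earlier description, but words it as an analysis in which "we exclude children whose treatment product was switched to the standard RUTF before the expiration date of their treatment product".

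The SAP does not name the expiring product, the switch date or the number of children switched. The primary analysis is ITT and the secondary analysis is CACE.

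**The concern.** There are three wordings but two analysis sets. The Statistical methods rule acts by calendar date on all three arms. The Table 5 and sub-group wordings remove only switched children, so only the arm whose product expired loses anyone. An analyst programming from Table 5 would run the analysis that the text says could induce bias.

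The stated direction makes this worse. A reader who believes that the narrow exclusion makes the affected arm look worse would take a non-inferior result under it as conservative. If that arm is experimental, the opposite is true.

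The SAP accepts that keeping switched children in ITT can bias results toward the null, and this is its only analysis aimed at that contamination. The switch is described in the past tense, so two open rules leave a choice to be made after the event.

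**Working it through.** **1. Direction.** A child is still on product at the switch only if not yet discharged. Children who never meet the recovery criteria can stay up to 12 weeks, while recovered children leave earlier. The children removed therefore include relatively more failures, and recovery among those kept rises. If this is done in one arm, that arm gains. If it is done in all arms with equal products, the difference is unchanged.

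**2. Check of the test formula.** Protocol Table 4: 306 analysed per arm, 77% recovery, 10-point margin, one-sided 0.05, stated power 90.0%. SE = √(2 × 0.77 × 0.23 / 306) = 0.0340. Power = Φ(0.10/0.0340 − 1.645) = 90.2%. This reproduces.

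**3. Closed-form illustration.** Assumptions: a share f of each arm enrols evenly over the 84 days before the switch; a child is still on product at the switch with probability stay/84; mean stay is 36.4 to 56 days if recovered (the MAM and SAM figures in SAP Table 4) and 60 to 84 days if not; one experimental product expires. Recovery among children kept = p(1 − f·Lr/84) / [p(1 − f·Lr/84) + (1 − p)(1 − f·Ln/84)], where Lr and Ln are the mean stays of recovered and non-recovered children.

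Example with f = 20%, Lr = 36.4, Ln = 84:
- Equal products, p = 0.77: 0.7033 / (0.7033 + 0.1840) = 79.3%. The Table 5 rule shows a spurious gain of 2.3 points; the all-arms rule shows none.
- Product truly 10 points worse, p = 0.67: 0.6119 / (0.6119 + 0.2640) = 69.9%. Under Table 5 the deficit shrinks to 77.0 − 69.9 = 7.1 points, and false non-inferiority is Φ((0.10 − 0.0714)/0.0369 − 1.645) = 19%. Under the all-arms rule the deficit is 79.3 − 69.9 = 9.4 points and the rate is 6.9%.

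| f | Spurious gain, Table 5, equal products (points) | False non-inferiority, Table 5 | False non-inferiority, all-arms date rule |
|---|---|---|---|
| 5% | 0.04 to 0.5 | 5.2 to 7.1% | 5.0 to 5.4% |
| 10% | 0.1 to 1.1 | 5.3 to 10.0% | 5.1 to 5.8% |
| 20% | 0.2 to 2.3 | 5.7 to 19% | 5.1 to 6.9% |
| 30% | 0.3 to 3.6 | 6.2 to 34% | 5.2 to 8.4% |

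If the control product were the one expiring, the sign reverses: −1.1 points at f = 10% and −3.6 at f = 30% (stays of 36.4 and 84 days).

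**4. Simulation on the SAP's relative margin.** True recovery 77% against 67.4%, a ratio of 0.875; lower one-sided 95% limit compared with 0.875. Assumptions: 360 per arm, uniform enrolment over 40 weeks, 8.5% default, gamma recovery times truncated to 2-12 weeks.
- Non-default failures stay 12 weeks, switch at weeks 36-44: Table 5 about 19-26% (ratio inflated to 0.91-0.92), all-arms date rule about 9-11%, enrolment-date rule about 5%.
- Same, switch at week 48: Table 5 about 12%, all-arms date rule about 6-7%.
- 60% of non-default failures leave within 6 weeks: Table 5 close to nominal (about 4-7%), all-arms date rule about 4-6%.

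**5. Length of stay.** This is also a SAP primary non-inferiority outcome. With identical products and a switch at weeks 36-44, the Table 5 rule shortens mean stay in the affected arm by about a day, against listed margins of 4.9 days (MAM) and 8 days (SAM).

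**The case against.** The best defence is that Statistical methods gives the only reasoned, operational rule, that the sub-group section refers back to it, and that Table 5 is a one-line label. The authors probably do intend the all-arms rule. That makes this a wording error, but it does not remove it: the other two places describe a different set of children.

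The large figures also need qualifying. The SAP says switched children had their own product for most of the course. In the simulation, with a switch at weeks 36-40, about half of them did not; at week 48 all did, and there the Table 5 rate is about 12%. Nor do all failures stay 12 weeks. SAP Table 4 gives 20.1% transfer and 12.5% non-response for SAM, so transfers are 20.1/(20.1 + 12.5) = 62% of those failures, and many could leave early. Long-stay selection is more plausible in MAM, where non-response is 28-32%. These qualifications stand.

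Four stronger inferences are not supported:
- *The bias certainly favours the new products.* The expiring product is not named. The SAP's concern about misclassification suggests an experimental one; if it was the control, the sign reverses. The wording also suggests one arm, so perhaps one comparison.
- *The non-inferiority conclusion is compromised.* The primary ITT analysis and its decision rule do not use either exclusion.
- *The all-arms date rule is as bad as Table 5.* It does select on time in treatment after randomization, but it is unbiased when products are equal and only modestly inflated at the margin.
- *CACE should count switched children as non-adherent.* It is true that "Adherence will be defined as attendance at all treatment visits", so CACE does not address the switch. But the change would make adherence depend on still being in treatment at the switch in one arm only. CACE should stay as it is.

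**Conclusion.** The contradiction and the reversed direction are established from the SAP text alone. The lean toward non-inferiority, and toward shorter stay, under the Table 5 rule holds if SMS-RUTF or S-RUTF was the expiring product.

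Its size cannot be fixed from the documents. It depends on how many children were switched, when, and how long failures stay in treatment, and it could be negligible. The simulated range at the margin is from about nominal to about 19-26% under Table 5, and about 4% to 11% under the Statistical methods rule. This should be fixed before unblinding; it does not threaten the primary analysis.

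**What to change.** Use one all-arms rule, worded identically, in Statistical methods, Table 5 and the sub-group section. At minimum, carry the Statistical methods rule into the other two. In the rationale, where the SAP has "making treatment outcomes spuriously appear worse in this arm", change worse to better. Report the expiring product, the switch date, and the number switched by arm and by MAM/SAM stratum.

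Preferably, define the set by enrolment date: exclude, in all arms, every child enrolled less than 12 weeks (the SAP's maximum treatment duration) before the switch. Enrolment date is fixed before randomization, so it cannot depend on arm or outcome, and every child kept has finished treatment by the switch.

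The minimum change costs only wording. The enrolment-date rule costs sample size in this sensitivity analysis. With 360 per arm over an assumed 40 weeks, a switch at week 36 keeps 360 × 24/40 = 216 per arm, and at week 44 it keeps 360 × 32/40 = 288. At week 40 it keeps 252: SE of log RR = √(2 × 0.23/(0.77 × 252)) = 0.0487, and power at equal 77% recovery is Φ(0.1335/0.0487 − 1.645) = 86%, against about 93% under the Statistical methods rule.
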